11.2.2 Serious Adverse Events (SAEs)

11.2.2.1 Site Requirements for Reporting SAEs and SUSAR's to HCRN

- SAEs will be reported from time of signed informed consent until 30 days after discontinuation of study drug(s) or until a new anti-cancer treatment starts, whichever occurs first.
- SAEs will be reported on the SAE Submission Form within 1 business day of discovery of the event.
- SAEs include events related and unrelated to the study drug(s).

Version Date: 18MAR2020 Confidential Page 30 of 41

- All SAEs will be recorded in the subject's medical record and on the appropriate study specific eCRF form within the EDC system.
- All SAEs regardless of relation to study drug will be followed until resolution to ≤ Grade 1 or baseline and/or deemed clinically insignificant and/or until a new anti-cancer treatment starts, whichever occurs first.

Suspected Unexpected Serious Adverse Reactions (SUSARs) are SAEs that qualify for mandatory expedited reporting to regulatory authorities where the SAE is suspected to be caused by the study treatment and is considered unexpected (ie, not defined as expected in the current IB clinical study protocol, or approved labeling for marketed drugs). After sponsor-investigator assessment, HCRN will report to the relevant regulatory authorities and forward a formal notification describing the SUSAR to investigators, according to regulatory requirements. Each investigator must then notify his or her IRB/IEC of the SUSAR as required by local regulatory authorities and in accordance with IRB/IEC policy.

The site will submit the completed SAE Submission Form to HCRN within 1 business day of discovery of the event. The form may be submitted to HCRN electronically to [contact]. The site investigator is responsible for informing the IRB and/or other local regulatory bodies as per local requirements. The original copy of the SAE Submission Form and the email correspondence must be kept within the study file at the study site.

Once the SAE has resolved (see resolution guidelines listed above), sites must submit a follow-up SAE Submission Form within a reasonable timeframe to HCRN electronically to [contact].

11.2.2.2 HCRN Requirements for Reporting SAEs and SUSARS to Astex

HCRN will report all SAEs to Astex Drug Safety at [contact] within 1 business day of receipt of the SAE Submission Form from a site. If the event is classified as a SUSAR, please clearly state in the notification to Astex as such, and include the date of SUSAR submission to regulatory agency. Follow-up information will be provided to Astex as it is received from site. Every quarter, Astex will provide a list of all SAEs to HCRN that were reported to Astex. HCRN will be asked to reconcile this list with the site's records, and report any discrepancies to Astex.

11.3 Sponsor-Investigator Responsibilities

HCRN will send a SAE summary to the sponsor-investigator **within 1 business day** of receipt of SAE Submission Form from a site. The sponsor-investigator will promptly review the SAE summary and assess for expectedness and relatedness.

11.4 Overdose

Record the actual dose of study drug administered in the source document and on the appropriate eCRF. Record any adverse clinical signs and symptoms associated with a potential overdose on the AE eCRFs. Report signs and symptoms of a potential overdose that meet SAE criteria to HCRN on the SAE form within 1 business day. Treat any AE (including SAE) based on standard care for the specific signs and symptoms. HCRN will report to Astex within 1 business day.

Version Date: 18MAR2020 Confidential Page 31 of 41

11.5 Pregnancy

Report any pregnancy that occurs in a subject or male subject's female partner during the time between the first dose of study treatment and 30 days after the last dose of study treatment. Record any occurrence of pregnancy on the Pregnancy Form and send information on the baby until the baby is 1 year old to HCRN who will report the information to Astex.

A subject must immediately inform the investigator if the subject or subject's partner becomes pregnant during the time between the first dose of study treatment and 30 days after the last dose of study treatment. Any female subjects receiving (study treatment) who become pregnant must immediately discontinue study treatment. The investigator should counsel the subject, discussing any risks of continuing the pregnancy and any possible effects on the fetus. Report any abortion and the reason for it, whether therapeutic, elective or spontaneous, to HCRN within 1 business day who will report to Astex within 1 business day.

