3. ELIGIBILITY CRITERIA

3.1 Inclusion Criteria

Subject must meet all of the following applicable inclusion criteria to participate in this study:

- 1. Male or female subjects, age \geq 18 years.
- 2. Histological or cytological diagnosis of small cell lung cancer. Subjects must have extensive stage disease, defined as disease beyond the ipsilateral hemithorax, mediastinum and ipsilateral supraclavicular area and including malignant pleural or pericardial effusion or hematogenous metastases.
- 3. Patients must have received first line therapy with a platinum-based chemotherapy. Patients should not have received more than 1 prior line of chemotherapy (could have received immunotherapy which does not count as chemotherapy).
- 4. ECOG PS 0-1
- 5. Measurable disease as per RECIST v1.1. Subjects may have bone-only disease. **NOTE:** Bone-only subjects are eligible if their disease can be documented/evaluated by bone scans, CT or MRI. Their disease will be assessed using MD Anderson criteria.(34) **NOTE:** Previously irradiated lesions are eligible as a target lesion only if there is documented progression of the lesion after irradiation.
- 6. Adequate bone marrow, liver, and renal function, as assessed by the following laboratory requirements:
 - o Hemoglobin $\geq 9.0 \text{ g/dL}$
 - o Absolute neutrophil count (ANC) $\geq 1,500/\text{mm}^3$
 - o Platelet count $\geq 100,000/\text{mm}^3$
 - o Total bilirubin \leq 1.5 x upper limit of normal (ULN). For subjects with Gilbert's Disease, total bilirubin \leq 3 x ULN

Version Date: 18MAR2020 Confidential Page 12 of 41

- o ALT and AST \leq 2.5 x ULN. For subjects with documented liver metastases, ALT and AST \leq 5×ULN
- o Estimated glomerular filtration rate (eGFR) \geq 60 mL/minute/1.73 m² as determined using the Cockcroft-Gault formula.
- 7. Women of child-bearing potential must not be pregnant or breastfeeding and must have a negative pregnancy test at screening.
- 8. Male and female subjects of child- bearing potential must agree to use contraception as outlined in Section 5.4 from the screening visit through 6 months after the last dose of study drug.

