5.4 Contraception

The following restrictions apply while the patient is receiving study treatment and for the specified times before and after:

Female patient of child-bearing potential

• Females of childbearing potential who are sexually active with a non-sterilized male partner must use at least 1 highly effective method of contraception from the time of screening and must agree to continue using such precautions for 180 days after the last dose of durvalumab + guadecitabine. Non-sterilized male partners of a female patient must use male condom plus spermicide throughout this period. Cessation of birth control after this point should be discussed with a responsible physician. Not engaging in sexual activity for the total duration of the drug treatment and the drug washout period is an acceptable practice; however, periodic abstinence, the rhythm method, and the withdrawal method are not acceptable methods of birth control. Female subjects should also refrain from breastfeeding throughout this period.

Male subjects with a female partner of childbearing potential

- Non-sterilized males who are sexually active with a female partner of childbearing potential must use a male condom plus spermicide from screening through 180 days after receipt of the final dose of durvalumab + guadecitabine or. Not engaging in sexual activity is an acceptable practice; however, occasional abstinence, the rhythm method, and the withdrawal method are not acceptable methods of contraception. Male subjects should refrain from sperm donation throughout this period.
- Female partners (of childbearing potential) of male subjects must also use a highly effective method of contraception throughout this period.

Females of childbearing potential are defined as those who are not surgically sterile (i.e., bilateral tubal ligation, bilateral oophorectomy, or complete hysterectomy) or post-menopausal.

Women will be considered post-menopausal if they have been amenorrheic for 12 months without an alternative medical cause. The following age-specific requirements apply:

- Women <50 years of age would be considered post-menopausal if they have been amenorrheic for 12 months or more following cessation of exogenous hormonal treatments and if they have luteinizing hormone and follicle-stimulating hormone levels in the post-menopausal range for the institution or underwent surgical sterilization (bilateral oophorectomy or hysterectomy).

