11.2 Reporting

11.2.1 Adverse Events

- AEs will be recorded from time of signed informed consent until 30 days after discontinuation of study drug(s) or until a new anti-cancer treatment starts, whichever occurs first.
- AEs will be recorded regardless of whether or not they are considered related to the study drug(s).
- All AEs will be recorded in the subject's medical record and on the appropriate study specific eCRF form within the EDC system.
- AEs considered related to study drug(s) will be followed until resolution to ≤ Grade 1 or baseline, deemed clinically insignificant, and/or until a new anti-cancer treatment starts, whichever occurs first.
- Asymptomatic laboratory abnormalities that do not require treatment will not be collected as adverse events.

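### Pregnancy reporting stops 30 days after the last dose although contraception is required for 180 days, so a pregnancy beginning on days 31-180 need not be reported.

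*Combined protocol and SAP*

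**What the plan says.** Section 11.5 (Pregnancy) sets one window and uses it twice. The site reports a pregnancy in a subject, or in a male subject's female partner, that occurs "during the time between the first dose of study treatment and 30 days after the last dose of study treatment". The subject has a parallel duty over the same window: "A subject must immediately inform the investigator if the subject or subject's partner becomes pregnant". Section 11.5 is also where infant outcome is captured: "Record any occurrence of pregnancy on the Pregnancy Form and send information on the baby until the baby is 1 year old". These reports go to HCRN and from there to Astex.

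The contraception requirement runs longer. Inclusion criterion 8 in section 3.1 requires it "from the screening visit through 6 months after the last dose of study drug", and the synopsis repeats this as its criterion 7. In section 5.4, female subjects "must agree to continue using such precautions for 180 days after the last dose", and non-sterilized male subjects with a partner of childbearing potential "must use a male condom plus spermicide from screening through 180 days after receipt of the final dose". Both sentences in section 5.4 go on to name durvalumab together with guadecitabine. The regimen in section 5.1 is guadecitabine and carboplatin.

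**The concern.** The protocol treats pregnancy as something to prevent for about six months after dosing, yet stops asking to hear about one after the first month. If contraception fails or is not used on, say, day 60, section 11.5 does not require the subject to tell the site, or the site to complete the Pregnancy Form or send information on the baby.

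What is at stake is safety information on an investigational hypomethylating agent combined with carboplatin, in subjects and in partners of male subjects. The trial's efficacy conclusions are not involved.

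**Working it through.** The plan states no figure to reproduce. The check compares time windows, with day 0 as the last dose.

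**Inputs**
- Pregnancy reporting by the site: first dose to day 30 (section 11.5).
- Subject's duty to inform the investigator: first dose to day 30 (section 11.5).
- Contraception, female and male subjects: to day 180 (section 5.4).
- Contraception, eligibility: to 6 months after the last dose of study drug (section 3.1, criterion 8). With 30-day months, 6 × 30 = 180 days, in line with section 5.4.

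**Arithmetic**
- Uncovered period = contraception window − reporting window = 180 − 30 = 150 days, that is days 31-180.
- Share of the post-dose contraception period = 150 / 180 = 83%.
- With the section 11.5 window extended to 180 days: 180 − 180 = 0 days uncovered.

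**Does another section cover days 31-180?**
- *Serious adverse events.* A congenital anomaly is a serious adverse event (section 11.1.2). Reporting ends 30 days after discontinuation, or earlier if new anti-cancer treatment starts (section 11.2.2.1). A birth defect after conception on day 31 or later would appear after that window has closed.
- *Adverse events.* Section 11.2.1 has the same cut-off.
- *Long-term follow-up.* The study calendar in section 7 lists imaging, survival status and subsequent therapy, with no pregnancy item.
- *Pregnancy testing.* It is required at screening only (section 7, footnote 3).
- *Sentences in section 11.5 without a time limit.* The instruction to record pregnancies on the Pregnancy Form and the instruction to report abortions carry no end date of their own. Each comes after a sentence that sets the 30-day window and is best read as inheriting it. Neither clearly creates a separate duty for days 31-180.

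**Does the 180-day premise hold despite the durvalumab wording?** The drug names in section 5.4 look carried over from another protocol; section 1.4 mentions durvalumab only in connection with a different guadecitabine study. Criterion 8 refers to section 5.4 for the methods of contraception but states its own duration, tied to study drug. The longer period therefore does not depend on the sentences that name the wrong drug.

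**The case against.** The strongest case for leaving the text alone is that contraception and reporting windows serve different purposes and nothing in the documents says they must be equal. Thirty days matches the adverse event and serious adverse event limits. No section justifies 180 days for guadecitabine plus carboplatin, so the documents show that the windows differ without showing which is wrong. Patients have previously treated extensive-stage disease, for which section 1.1 puts median survival at less than a year, so pregnancies will be very few. After new anti-cancer therapy starts, attribution becomes harder.

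Much of this stands: it keeps the point minor. It does not remove it. Pregnancy already has its own section, its own form and infant follow-up to age 1, so the protocol does not handle it as an ordinary adverse event. Reporting through the required contraception period does not depend on settling fetal risk on days 31-180. Shortening contraception would depend on it, and the documents give no data for that.

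Three stronger readings are tempting and are not supported.
- A reader might take the phrase "Not engaging in sexual activity for the total duration of the drug treatment and the drug washout period" in section 5.4 as the protocol's own acknowledgement that exposure matters through day 180. Washout is mentioned there once, without definition or length, in a bullet that also names the wrong drug. It cannot carry that inference.
- A reader might infer that a pregnancy on days 31-180 will receive no Pregnancy Form and no follow-up. The text removes the duty; it does not forbid a site from reporting.
- A reader might take 83% as the share of pregnancies missed. It is a share of days, and the documents give no basis for an expected number.

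**Conclusion.** The mismatch is real and follows from the text. For 150 of the 180 post-dose days on which contraception is required, the visible protocol requires neither reporting of a new pregnancy nor follow-up of the infant. This is a cheap improvement to safety capture at the lowest level of importance. Events will be rare, and no sample size, error rate or efficacy analysis is touched.

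The conclusion rests on two assumptions: that the sentences in section 11.5 without a time limit inherit the 30-day window, and that no other document extends it. Consent pages are not part of this copy, so any duty stated there cannot be checked.

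**What to change.** - In both places in section 11.5, change 30 days to 180 days after the last dose of study treatment.
- Add one sentence stating that this applies despite the 30-day cut-off for adverse and serious adverse events in sections 11.2.1 and 11.2.2.1.
- Add a pregnancy question to the existing long-term follow-up contacts, up to and including the first one on or after day 180, asking about any pregnancy that began through day 180. Section 7, footnote 10 already provides contacts every 2 months for 1 year without progression, or every 3 months for 1 year after it, and allows them by phone. For subjects still in follow-up, no visit needs to be added. The question would also pick up a conception shortly before day 30 that is recognised only after the safety visit.
- In the same amendment, correct the drug names in section 5.4 to the regimen given in this trial.

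The cost is a protocol amendment notified to the IRB (section 15.1), one eCRF item and probably matching consent wording, because section 11.5 places a duty on the subject. The Pregnancy Form already exists. The drawback is about five more months of pregnancy reporting (150 / 30 = 5), some of it after new anti-cancer therapy has started, when attribution to study treatment is harder.

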11.6 HCRN Responsibilities to FDA

HCRN will manage the Investigational New Drug Application (IND) associated with this protocol on behalf of the sponsor-investigator. HCRN will cross-reference this submission to the Astex's parent IND at the time of submission. Additionally, HCRN will submit a copy of these documents to Astex and IU DSMC at the time of submission to FDA.

For protocols conducted under an IND, HCRN will be responsible for all communication with the FDA in accordance with 21CFR312 including but not limited to the 7 and 15 Day Reports, as well as an Annual Progress Report. Additionally, HCRN will submit a copy of these reports to Astex and IU DSMC at the time of submission to FDA.

11.7 IND Safety Reports Unrelated to this Trial

Astex will provide to HCRN IND safety reports from external studies that involve the study drug(s) per their guidelines. HCRN will forward safety reports to the sponsor-investigator who will review these reports and determine if revisions are needed to the protocol or consent. HCRN will forward these reports to participating sites **within 1 business day** of receiving the sponsor-investigator's review. Based on the sponsor-investigator's review, applicable changes will be made to the protocol and informed consent document (if required). All IND safety reports will also be made available to sites via the EDC system.

Upon receipt from HCRN, site investigators (or designees) are responsible for submitting these safety reports to their respective IRBs, as per their IRB policies.

Version Date: 18MAR2020 Confidential Page 32 of 41

12 STATISTICAL METHODS

Statistical analysis of this study will be the responsibility of the Department of Biostatistics at Indiana University School of Medicine. Parameter estimates and relevant summary statistics will be reported for both efficacy and safety outcomes. Continuous variables will be summarized by means, medians, minima, maxima, and standard deviations. Categorical variables will be summarized by frequencies and percentages. Missing data will not be imputed. Additional exploratory analysis will be conducted when appropriate. Changes from the analysis plan will not require an amendment to the protocol unless it changes a significant feature in the protocol; however, all changes from the original analysis plan will be documented in the final study report. The statistical analysis methods are outlined below.

12.1 Study Design

This is a Phase II study evaluating the efficacy and safety of Guadecitabine in combination with carboplatin in Extensive Stage Small Cell Lung Cancer. The statistical analyses will be primarily in the chemotherapy-sensitive group. Chemotherapy-resistant patients will also be enrolled but will be described separately. Chemo-sensitivity is defined as a response to initial platinum therapy that lasts ≤ 90 days. Chemo-resistance is defined as response to platinum therapy that lasts ≤ 90 days.

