1. BACKGROUND AND RATIONALE

1.1 SCLC General Background

Small cell lung cancer (SCLC) is an aggressive malignancy characterized by early hematogenous spread, initial chemotherapy sensitivity followed almost uniformly with rapid resistance and high genetic instability(1). The majority of patients present with extensive stage disease and platinum based chemotherapy remains the standard first line treatment(2). Chemo-sensitivity is defined as a response to initial platinum therapy that lasts ≥90 days. Chemo-resistance is defined as response to platinum therapy that lasts <90 days. Initial response rates to platinum based chemotherapy in extensive stage SCLC are 65-70%. Second line treatment options for SCLC include a number of chemotherapy agents, all with response rates of 20-30% and minimal survival benefit(3). Topotecan remains the only FDA approved second line therapy in SCLC with low response rates and minimal improvement in survival(4-6). Median survival of extensive stage SCLC patients therefore remains less than a year. SCLC has lagged behind many malignancies with limited improvements in the development of novel therapies.(7, 8)

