3.2 Exclusion Criteria

- 1. Platinum refractory disease defined as disease progression during first line platinum containing chemotherapy regimen. Progression following platinum based therapy is allowed.
- 2. Prior therapy with a hypomethylating agent.
- 3. Previously untreated (non-irradiated), symptomatic brain metastases. No prior treatment is required for non-symptomatic brain metastases. Previously treated symptomatic brain metastases are permitted.
- 4. Unstable or clinically significant concurrent medical condition, psychiatric illness or social situation that would, in the opinion of the investigator, jeopardize the safety of a subject and/or their compliance with the protocol.
- 5. Clinically significant acute infection requiring systemic antibacterial, antifungal, or antiviral therapy. (Suppressive therapy for chronic infections allowed, for example: Subjects with HIV/AIDS with adequate antiviral therapy to control viral load would be allowed. Subjects with viral hepatitis with controlled viral load would be allowed while on suppressive antiviral therapy.)
- 6. Hypersensitivity to (IMP) or components of the study treatment regimen.
- 7. Treated with any investigational drug within 3 weeks of first dose of study treatment.
- 8. Pregnant or breastfeeding.
- 9. Second malignancy currently requiring active therapy except breast or prostate cancer stable on or responding to endocrine therapy.

Version Date: 18MAR2020 Confidential Page 13 of 41

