4. SUBJECT REGISTRATION

All subjects must be registered through HCRN's electronic data capture (EDC) system prior to starting protocol therapy. Subjects must begin therapy **within 7 business days** of registration.

Registered patients will be assigned to chemo-sensitive or chemo-resistant group based on the time of disease progression since the completion of platinum containing chemotherapy. Chemosensitivity is defined as a response to initial platinum therapy that lasts ≥ 90 days. Chemoresistance is defined as response to platinum therapy that lasts < 90 days.

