12.3 Sample Size and Accrual

For the chemo-sensitive group, when the sample size is 24, a non-parametric test (single-group) with a one-sided 0.10 significance level will have 80% power to detect the difference between a median survival of 3.0 months vs 6.0 months assuming an accrual period of approximately 12 months and maximum follow-up of 24 months (i.e. would allow for up to 12 months of follow-up after accrual ends). With 24 in the chemo-sensitive group, we expect to enroll approximate 34 subjects total, thus will have approximately 10 chemo-resistant patients to generate pilot data.

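### Section 12.1, as it reads, gives both platinum groups the same 90-day rule, and Section 4 neither ties its clock to its cut-off nor places patients without a first-line response

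*Combined protocol and SAP*

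**What the plan says.** Three sections of the combined protocol and SAP define the two groups.

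- **Section 1.1** (background): "Chemo-sensitivity is defined as a response to initial platinum therapy that lasts ≥90 days"; resistance is a response lasting less than 90 days.
- **Section 4** (registration): patients are "assigned to chemo-sensitive or chemo-resistant group based on the time of disease progression since the completion of platinum containing chemotherapy". The next sentences repeat the Section 1.1 definitions, starting with "Chemosensitivity is defined as a response to initial platinum therapy that lasts ≥ 90 days".
- **Section 12.1** (statistical methods): "Chemo-sensitivity is defined as a response to initial platinum therapy that lasts ≤ 90 days", followed by "Chemo-resistance is defined as response to platinum therapy that lasts ≤ 90 days".

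Section 3.2 determines who can reach this classification. It excludes "Platinum refractory disease defined as disease progression during first line platinum containing chemotherapy regimen" and adds "Progression following platinum based therapy is allowed".

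The grouping carries the main analysis. Section 12.3 sizes the trial on it ("For the chemo-sensitive group, when the sample size is 24, a non-parametric test (single-group) with a one-sided 0.10 significance level"). Section 12.6.1 tests PFS against 3 months in the chemo-sensitive group alone, and Section 12.6.2 reports the secondary analyses separately by group.

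**The concern.** There are two separate problems.

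1. The Section 12.1 rule is identical for both groups and runs opposite to Sections 1.1 and 4 for the sensitive group. Section 12.1 is where an analyst would look for the definition of the primary analysis group.
2. Section 4 does not depend on any symbol being read correctly, and it names two different quantities. One is an interval that starts at platinum completion. The other is the duration of a response, with no stated start. The section does not say how they fit together, or what happens to a patient who had no response but did not progress on platinum.

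At stake is who enters the primary test and which column each patient's secondary results appear in. Both should follow from the text without interpretation.

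**Working it through.** **Step 1. The plan's own figure.** Inputs from Sections 12.3 and 12.6.1: n = 24, one-sided alpha 0.10, medians 3.0 and 6.0 months, about 12 months' accrual, maximum follow-up 24 months, sign test for censored data. I assume exponential PFS. The probability of being progression-free beyond 3 months is then 0.50 under the null and 2^(−3/6) = 0.7071 under the alternative. The last patient has 12 months of follow-up, so no administrative censoring falls before 3 months.

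Power = Φ{[(0.7071 − 0.5) − 1.2816 × 0.5/√24] / [√(0.7071 × 0.2929)/√24]} = Φ{(0.2071 − 0.1308)/0.0929} = Φ(0.82) = 0.794.

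This agrees with the stated 80%. An exact binomial version (reject at 16 or more of 24) has alpha 0.076 and power 0.751. The expected split also agrees: 0.70 × 34 = 23.8, that is 24 and 10. None of these figures uses the 90-day wording, so none changes with it.

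**Step 2. The definitions side by side.**

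| Place | Quantity | Clock start | Sensitive | Resistant |
|---|---|---|---|---|
| 1.1 | duration of response | not given | ≥ 90 days | < 90 days |
| 4, assignment sentence | time to progression | platinum completion | no cut-off | no cut-off |
| 4, definition sentences | duration of response | not given | ≥ 90 days | < 90 days |
| 12.1 | duration of response | not given | ≤ 90 days | ≤ 90 days |

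**Step 3. Illustrative patients (assumed dates).**

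- *Response lasting 60 days.* Section 12.1 puts the patient in both groups; Sections 1.1 and 4 say resistant.
- *Response lasting 120 days.* Section 12.1 puts the patient in neither group; Sections 1.1 and 4 say sensitive.
- *Response first seen 40 days before platinum completion, progression 60 days after it.* From completion the interval is 60 days (< 90, resistant). From onset of response it is 40 + 60 = 100 days (≥ 90, sensitive). The text does not say which start applies to the 90 days.
- *First-line stable disease, progression 120 days after completion.* The completion clock with a 90-day cut-off gives sensitive (120 ≥ 90). The definition sentences require a response, so they give neither group.

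**Step 4. Is the last patient eligible?** Section 3.2 excludes progression during first-line platinum and allows it afterwards, so stable disease followed by later progression is not excluded. Response to earlier treatment is not defined. For the trial's own endpoints, Sections 2.2.2, 9.8.1 and 12.2.2 count response as complete plus partial response, and stable disease enters only the disease control rate. One therefore cannot simply assume that response includes stable disease.

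**Step 5. How much could one patient matter?** Assume no censoring before 3 months. In exact form, 16 of 24 gives p = 0.076; with one of those 16 moved out, 15 of 23 gives p = 0.105. In the normal form, z = (S − 0.5)/√(S(1 − S)/n), the same move takes p from 0.042 to 0.063 and the test still rejects. In that form a move across 0.10 needs the opposite change: 15 of 24 gives p = 0.103, and removing one early progressor gives 15 of 23, p = 0.063. This is what any test with 24 patients does near its boundary. It is not evidence that the result would be wrong.

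**The case against.** The strongest reply has three parts.

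**The symbols.** The Section 12.1 signs come from text read out of a PDF and may be misread. Sections 1.1 and 4 agree with each other, and Section 4 is where patients are actually assigned, so the intended direction is recoverable. This stands. A reader might infer that the plan has no usable cut-off or that the misprint is proven; the documents support neither.

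**The two bases in Section 4.** The assignment sentence has no cut-off and the definition sentences have no clock, so the natural reading is that one supplies the clock and the other the threshold. On that reading the 60-versus-100-day conflict disappears. It is a fair reading, and it rules out calling the sentences necessarily competing rules. It also means the assignment sentence does not classify anyone by itself. But the protocol nowhere states this reading, and it still leaves the stable-disease patient without an explicit group.

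**The consequences.** A reader might infer that the primary test is compromised, or that it is the only hypothesis test in the plan. Neither follows. Section 12.6.3 also plans t-tests and Wilcoxon tests on biomarkers, so the correct statement is that the chemo-sensitive group has the only primary-endpoint test. Groups are assigned at registration, before outcomes are known, and the p-value shifts in the working show only general sensitivity at n = 24.

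**Conclusion.** The point holds as a defect in the definition of the primary analysis group that should be fixed. As it reads, Section 12.1 cannot separate the groups and contradicts Sections 1.1 and 4; this part is conditional on the source PDF printing the same sign twice. The Section 4 part does not depend on the symbols: the link between clock and cut-off is left to the reader, and an eligible patient with first-line stable disease has no stated group.

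The number of patients affected cannot be determined. Section 1.1 gives initial response rates of 65–70%, so 30–35% of first-line patients do not respond. An unknown share of those are excluded as refractory, so this shows only that the case is not far-fetched; it is not an estimate. The documents give neither a misclassification rate nor a median PFS for resistant patients, so no loss of power can be claimed. N, alpha and the stated 80% power are unaffected.

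**What to change.** 1. Check Section 12.1 against the source PDF. If it prints ≤ for both groups, reconcile it with Sections 1.1 and 4.
2. Use one definition in Sections 1.1, 4 and 12.1, with one stated clock origin and the 90-day cut-off. The Section 4 assignment sentence already offers an interval from platinum completion to progression; the sponsor should confirm whether that is the intended basis.
3. Word it so that eligible patients without a complete or partial response to first-line platinum are also classified.
4. State which progression counts when immunotherapy was also given, since inclusion criterion 3 allows it without counting it as chemotherapy.
5. Confirm that the dates the rule needs are captured. Footnote 1 of the Study Calendar requires prior treatment to be documented but does not name the dates of platinum completion or first-line progression.

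The cost is a wording change in three sections and possibly a case report form check. Sample size, alpha and power stay as they are.
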